13.6.2 Primary Endpoint(s)

Blinded Phase:

The primary endpoint is the change in number of seizures* during the treatment period (maintenance and titration) compared to baseline in patients taking GWP42003-P compared with placebo.

*Seizures include: focal motor seizures without impairment of consciousness or awareness; focal seizures with impairment of consciousness or awareness; focal seizures evolving to bilateral generalized convulsive seizures and generalized seizures (tonic-clonic, tonic, clonic or atonic) that are countable.

Data will be analyzed using negative binomial regression on the sum of the seizure counts during the treatment period. However, seizure frequency (average per 28 days) and percentage change in seizure frequency will be presented using summary statistics. A mixed effect model with repeated measures will be performed modelling the observed number of seizures in the baseline period and treatment period implemented within the framework of general linear models using the negative binomial response distribution. The model will include stratified age group (1–6 years, 7–11 years, 12–17 years and 18–65 years), time, treatment arm and treatment arm by time interaction as fixed effects and patient as a random effect. The log transformed number of days in which seizures were reported will be included as an offset. The time variable corresponds to an indicator for the baseline period and treatment period. The estimated ratio of least squares means for treatment period to baseline period and 95% confidence intervals (CIs) will be presented for each treatment arm. In addition, the estimated ratio of each GWP42003-P group to placebo and 95% CIs will be presented along with the p-value testing the null hypothesis that this ratio is 1.

The hypothesis testing approach for controlling the Type I error is described in [Section 13.6](#) and [Table 13.6-1](#).

If a patient withdraws from the study, then the primary analysis variable will be calculated from the available data, during the treatment period, prior to the patient withdrawing.

Open-label Extension:

The primary endpoint is the safety of GWP42003-P, evaluated by assessing the incidence, type and severity of AEs. Data will be presented as per [Section 13.6.5.2](#).

Study Code: GWEP1521
 EudraCT Number: 2015-002154-12
 Protocol V8 23Apr19

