7.2 Randomization

The allocation of IMP to treatment number will be done according to a randomization schedule produced by an independent statistician. The randomization schedule will be held centrally and not divulged to any other person involved in the study until the database has been locked and unblinding authorized by the relevant GW personnel. For access to blinded treatment assignment, see [Section 8.5](#).

The randomization will be stratified by age group (1–6 years, 7–11 years, 12–17 years and 18–65 years).

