13.1 Sample Size, Power and Significance Levels

Blinded Phase:

A total of 210 patients will be enrolled. The 210 patients will be randomly allocated to one of four treatment groups (GWP42003-P 25 mg/kg/day, GWP42003-P 50 mg/kg/day, placebo 25 mg/kg/day dose volume equivalent, or placebo 50 mg/kg/day dose volume equivalent) at a 2:2:1:1 ratio. The placebo groups will be pooled for the analyses of efficacy.

If it is assumed that patients in the placebo group will experience a mean reduction in seizure frequency of 15% (from baseline), patients receiving GWP42003-P will experience at least a 50% reduction in seizures and a common standard deviation of 60%, then this sample size of 70 patients per group will be sufficient to detect a difference in response distributions with 90% power. This test is based on a two-sided non-parametric Wilcoxon-Mann-Whitney test for continuous response data with a 5% significance level.

Open-label Extension:

All patients who wish to continue on IMP following the blinded phase.

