For number of seizure-free days, use of rescue medication, number of episodes of *status epilepticus* (only if there is a sufficient number of patients with data), Vineland-II, Wechsler scales, CBCL, ABCL, SCQ, QOLCE and QOLIE-31-P scores, the data will be summarized at baseline and over the treatment period, and at each time-point (or 28-day period, as appropriate) during the maintenance period. Changes from baseline to the average over the treatment period (or at end of study) will be analyzed using ANCOVA (or appropriate non-parametric methods if data are found to be not normally distributed). The models will include baseline and age group as covariates and treatment group as fixed factor. The treatment difference, together with the 95% CIs will be presented.

The changes in composite focal seizure score, change in total seizures, the number of seizures by subtype and the number of ‘other’ seizures will be analyzed using the same analysis as the primary endpoint.

SGIC-SD/CGIC-SD, SGIC/CGIC and PGIC assessments recorded at the end of treatment will be analyzed with ordinal logistic regression using the proportional odds model.

Study Code: GWEP1521
EudraCT Number: 2015-002154-12
Protocol V8 23Apr19

Changes from baseline for IGF-1 levels will be summarized by treatment group and plotted against the Tanner Stages, weight, and height.

Tanner Stages will be evaluated and summarized descriptively at each time-point in terms of frequency and proportions. Number (%) of patients with changes in Tanner Stages will be summarized by treatment group.

In order to explore the robustness of the primary analysis, further sensitivity analysis (in addition to that already detailed in [Section 13.6.2.1](#)) may be specified in the SAP.

Open-label Extension:

Secondary endpoints will be summarized across time, using appropriate statistical methods. Descriptive statistical methods will be used throughout. There will be no formal hypothesis testing.

Exploratory Endpoints:

Antiepileptic Efficacy Measures:

- Change in composite focal seizure score (frequency × severity).
- Change in number of seizures by subtype.
- Change in use of rescue medication.
- Change in the number of episodes of *status epilepticus* (convulsive and non-convulsive).
- Changes in duration of seizure subtypes as assessed by the Subject Global Impression of Change in Seizure Duration (SGIC-SD) or the Caregiver Global Impression of Change in Seizure Duration (CGIC-SD).

TAND:

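### The primary model's age term drops out of the tested ratio and its free arm main effect under-uses the baseline counts: an efficiency gain is available, but the test is valid as planned

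*Protocol*

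**What the plan says.** Section 13.6.2 takes each patient's baseline count and treatment-period count as two observations, with log reported days as offset. The fixed effects are four-level age group plus "time, treatment arm and treatment arm by time interaction as fixed effects and patient as a random effect". The reported results are each arm's treatment-to-baseline ratio and the ratio of each active arm to placebo, tested against 1. There is no age-by-time term, and baseline is not a covariate.

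Under section 13.6.3 the same analysis serves total seizures. The model therefore governs tests 1, 3, 6 and 8 of Table 13.6-1, where one failure stops everything after it.

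Section 7.2 states: "The randomization will be stratified by age group". The rationale in Amendment 6 (Change in Primary Endpoint Analysis Method and Wording) lists the ability to take in the stratification factor among the reasons for leaving the Wilcoxon test.

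**The concern.** Two features of the stated model make less of the collected data than they could.

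- **Age.** A main effect of age moves a patient's baseline and treatment-period means by the same factor. The tested quantity compares the two periods within patients, so that factor divides out. The stratification factor is in the model but does not act on the confirmatory contrast, which sits awkwardly with the Amendment 6 rationale.
- **Baseline.** Baseline is observed before randomization, so arms share the same expected baseline mean. A free arm main effect ignores this. The estimate then behaves like a change score: the whole chance difference in baseline is subtracted, however weakly baseline predicts the outcome.

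At stake is the width of the confidence interval in four of the eight confirmatory tests, including the first gate.

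**Working it through.** **1. The plan's own power figure, as a reference point.** Inputs from section 13.1: placebo, "patients in the placebo group will experience a mean reduction in seizure frequency of 15% (from baseline"); active, "experience at least a 50% reduction in seizures and a common standard deviation of 60"%; allocation, "placebo 50 mg/kg/day dose volume equivalent) at a 2:2:1:1 ratio" with placebo pooled, so 210 × 2/6 = 70 in each active arm and 35 + 35 = 70 on placebo. The claim is: "then this sample size of 70 patients per group will be sufficient to detect a difference in response distributions with 90% power". Noether's formula for the Wilcoxon test gives:

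- p = Φ(35 / (60√2)) = 0.660
- n = (1.960 + 1.282)² / (6 × 0.160²) = 68.4, so 69 per group
- power at 70 = Φ(√(6 × 70) × 0.160 − 1.960) = 0.906

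The figure reproduces. It concerns the Wilcoxon test and supplies no dispersion or correlation for the negative binomial model.

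**2. Age.** In the linear analogue of the model (two periods, random patient effect, simulated data with a strong age effect on level), the arm-by-time estimate for one active arm was:

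| Model | Estimate | SE |
|---|---|---|
| without age | −0.4757 | 0.1673 |
| with age main effect | −0.4757 | 0.1673 |
| with age and age by time | −0.4720 | 0.1691 |

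The first two rows are identical and equal the raw difference in mean change. With unequal period variances, the rows without and with the age main effect again agree (−0.3035, SE 0.1323). In fitted negative binomial mixed models, estimates with and without age correlated at 0.999 or more and differed by at most 0.02 on the log scale. The third row shows that age by time gains nothing when age does not predict change; here the SE rose by about 1% (0.1691 / 0.1673 = 1.011).

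**3. Baseline.** Let s1 and s2 be the log-scale SDs at baseline and on treatment, and ρ their correlation.

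- Free arm main effect: slope 1, variance proportional to s1² + s2² − 2ρ·s1·s2
- Common baseline mean: slope ρ·s2/s1, variance proportional to s2²(1 − ρ²)
- Share saved = (s1 − ρ·s2)² / (s1² + s2² − 2ρ·s1·s2), which is (1 − ρ)/2 when s1 = s2

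With equal SDs the saving is 30% at ρ = 0.4, 20% at 0.6, 10% at 0.8 and 5% at 0.9. With s2/s1 between 0.8 and 1.25 it runs from 0 to 46%. The protocol fixes none of these inputs.

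**4. The actual model type.** Negative binomial counts were simulated over 28 and 112 days with the eight-seizure entry rule of criterion 6.1.11 and 70 per arm. The planned model was then compared with the same model without the arm main effect.

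- Assumed dispersions 0.1 to 0.7, 240 runs per setting: variance ratio 0.78 to 0.99, no bias, power up by about 1 to 9 points.
- Smaller runs (100 per set, rate ratio 0.50/0.85 = 0.588, patient log-SD 1.0), two sets per setting: 0.85 and 0.89 at dispersion 0.3; 0.83 and 0.77 at 0.4; 0.89 and 0.77 at 0.6. The spread within a setting shows the simulation error.
- Further runs of 100: 0.92 at dispersion 0.4 in both periods, and 1.05 (no gain) with dispersion 0.1 at baseline and 0.7 on treatment.

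**5. What the upper end would mean.** Applied to the reference power of step 1, a 22% variance reduction gives Φ(3.279/√0.78 − 1.960) = 0.960, or the planned precision from 70 × 0.78 ≈ 55 per group. A reduction near 0 leaves 0.906.

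**The case against.** The strongest reply is that nothing here is wrong. The endpoint is declared as a change against baseline, the model estimates exactly that, and it is unbiased. Section 13.6.2.1 already plans a rank ANCOVA and a log-count ANCOVA adjusted for baseline and age, and the responder test is stratified by age. The gain rests on assumed inputs and vanished in one setting with very unequal dispersion. All of this stands, and it makes the point one of efficiency. It does not remove it: sensitivity analyses cannot pass test 1, and the model is fixed in the protocol itself.

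A further caution is that equal baseline means are guaranteed for all randomized patients, whereas the ITT set in section 13.3 also requires dosing and post-baseline data. The constraint relies on such exclusions being few or unrelated to arm.

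Four stronger readings are tempting and are not supported:

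- **That baseline cancels.** It does not. It is one side of the tested ratio; what cancels is the patient effect and anything acting equally on both periods.
- **That a fixed loss of 11 to 22% follows.** With equal SDs it would need ρ between 0.56 and 0.78, which the protocol does not state. Nor does it measure the cost of the age term, which is zero unless age predicts change.
- **That negative binomial regression on log baseline rate and age is an equivalent remedy.** Against the planned model its variance ratio was 1.07 to 1.11 in one set of simulations and 0.94 to 1.29 in another.
- **That age was left out of the CGIC/SGIC model.** Section 13.6.3 says only: "SGIC-SD/CGIC-SD, SGIC/CGIC and PGIC assessments recorded at the end of treatment will be analyzed with ordinal logistic regression using the proportional odds model". That names a method and lists no covariates; these may properly be settled in the SAP.

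**Conclusion.** The point holds as an available improvement. The age main effect does not adjust the tested arm-by-time ratio, exactly so in the linear analogue and almost exactly in the negative binomial model. The free arm main effect leaves baseline information partly unused. Validity, type I error and the estimate itself are not in question.

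The size is a variance reduction of roughly 0 to 22% and about 1 to 9 points of power, assuming 70 per arm, the eight-seizure entry rule and dispersions of 0.1 to 0.7. The gain comes from the common baseline mean. No benefit from age by time has been shown; it helps only if age predicts the change.

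**What to change.** In section 13.6.2, and through it for total seizures, keep the negative binomial mixed model, the offset and the random patient effect. Remove the arm main effect so that all arms share one baseline mean and differ only in the treatment period. Add age group by time beside the age main effect. The per-arm treatment-to-baseline ratios and the active-to-placebo ratios can still be reported as planned. The model with the free arm main effect can be kept as a sensitivity analysis.

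The cost is one changed model statement, to be fixed before unblinding, and three more fixed-effect parameters for age by time against one fewer for each active arm. No new data, visits or patients are needed. If a gain is quoted in support, give it as a range over stated dispersions and correlations.

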13.6.2.1 Sensitivity Analysis for the Primary Endpoint

Blinded Phase:

The following sensitivity analyses will be conducted for the primary endpoint for the blinded phase:

- Wilcoxon rank-sum test on percentage change from baseline in seizure frequency during the treatment period. An estimate of the median differences between each GWP42003-P group and placebo, together with approximate 95% CIs, will be calculated using the Hodges–Lehmann approach.
- Primary endpoint analysis repeated using the PP analysis set.
- Primary endpoint analysis repeated using the maintenance period (Day 29 to the end of the evaluable period) rather than the treatment period.
- Primary endpoint analysis repeated using the worst case of last observation carried forward (LOCF), next observation carried backward (NOCB) and the mean from the non-missing data for each patient to impute missing data arising from unreported days in IVRS.
 - Any intermittent missing data for the number of seizures arising from unreported days in IVRS will be imputed using the worst (highest number of seizures) of the following for each patient: LOCF, NOCB and the mean daily number of seizures during the treatment period based on non-missing data:

$$\text{Number of seizures} \div \text{Number of reported days in IVRS.}$$
- A rank ANCOVA on percentage change from baseline in number of seizures (average per 28 days) during the treatment period.
 - The ranks of the percentage change from baseline and the baseline number of seizures (average per 28 days) will be calculated. The rank of the percentage change from baseline will then be analyzed using an ANCOVA model with the rank of the baseline number of seizures (average per 28 days) and age group (1–6 years, 7–11 years, 12–17 years and 18–65 years) as covariates and treatment group as a fixed factor. The estimated least squares means, treatment differences, together with the 95% CIs and p-value will be presented.
- ANCOVA of log transformed number of seizures (average per 28 days) during the treatment period.

Study Code: GWEP1521
EudraCT Number: 2015-002154-12
Protocol V8 23Apr19

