2 RATIONALE

This clinical protocol amendment 6 (will be incorporated into the Protocol creating Clinical Protocol Version 7, Date 06 September 2018) addresses the following issue(s): **Change in Primary Endpoint Analysis Method and Wording**

A suitable modelling approach to seizure count data would be superior to the non-parametric Wilcoxon rank-sum test as it allows estimates of effect size that are meaningful and can easily be interpreted, can incorporate the stratification variable, can be used to explore potential effect modifying variables, and might be expected to provide more power. Exploration of data from previous epilepsy trials in Dravet syndrome and Lennox–Gastaut syndrome indicate that modelling of seizure counts implemented within the framework of general linear models, using the negative binomial response distribution, provides an optimal fit to the data. Additionally, this modelling approach also has advantages such as being able to model the exact seizure count during the treatment period, incorporating the number of days with data as an offset within the model, without requiring the seizure count to be transformed into a frequency prior to analysis. For example, if there are patients who withdraw early in the trial prior to experiencing a seizure, calculating a seizure frequency and percentage change could lead one to assume a patient had a 100% reduction in seizure frequency when in fact they might not have been evaluated for a sufficient amount of time. The negative binomial model accounts for the number of days each patient is evaluated for and so is not impacted. Accordingly, the proposed primary analysis method has been updated from the Wilcoxon rank-sum test to a negative binomial regression analysis.

As percentage change does not apply to negative binomial regression, the primary endpoint wording has been changed throughout the protocol to remove the words ‘percentage change’ as follows:

‘Percentage change from baseline in number of TSC-associated seizures
(average per 28 days) during the treatment period (maintenance and titration) in
patients taking GWP42003-P compared with placebo.’*

has been amended to:

‘Change in number of TSC-associated seizures during the treatment period
(maintenance and titration) compared to baseline in patients taking GWP42003-P
compared with placebo.’*

Similar changes have been made for percentage change in other seizure types under key secondary, other secondary, and exploratory endpoints.

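### As worded in Section 13.6.2, the primary model's offset counts days with seizures, whereas the protocol's own rationale calls for days with IVRS data

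*Protocol*

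**What the plan says.** Section 13.6.2 describes a repeated-measures negative binomial model "modelling the observed number of seizures in the baseline period and treatment period", with age group, period, treatment and treatment-by-period as fixed effects and patient as a random effect. On exposure it has one sentence: "The log transformed number of days in which seizures were reported will be included as an offset".

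Three other places bear on it.

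- **Amendment 6, Section 2 (Rationale)**, which introduced this model and this sentence, describes the approach as "incorporating the number of days with data as an offset within the model". It discusses patients who leave before having a seizure and concludes: "The negative binomial model accounts for the number of days each patient is evaluated for and so is not impacted".
- **Section 13.6.2.1** treats days without a call as missing data: "Any intermittent missing data for the number of seizures arising from unreported days in IVRS will be imputed". Its daily mean divides by "Number of reported days in IVRS".
- **Section 13.6.3** says that the composite focal seizure score, total seizures, seizures by subtype and 'other' seizures "will be analyzed using the same analysis as the primary endpoint".

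**The concern.** In plain English, a day on which seizures were reported is a day with at least one seizure. A day on which the caregiver called and reported none is not such a day. With that denominator the model no longer measures seizure frequency, which is what the primary objective in Section 2.1 concerns. It measures how many seizures occur on a day that has any.

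A simple case shows the difference. Suppose a patient has one seizure on each of 28 baseline days, then one seizure on 56 of 112 treatment days.

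- Observed days: (56/112) / (28/28) = 0.50.
- Seizure-days: (56/56) / (28/28) = 1.00.

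The halving disappears.

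The offset enters tests 1 and 3 of Table 13.6-1 directly and, through Section 13.6.3, tests 6 and 8. Test 1 is the gate: if it fails, all testing stops. The sensitivity analyses that repeat the primary analysis (per protocol, maintenance period, 4-week windows, worst-case imputation) would inherit the same offset.

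**Working it through.** **Inputs from the protocol.** Mean reduction of 15% on placebo and 50% on active, SD 60%, 70 per group (Section 13.1); minimum of 8 seizures in 28 days (criterion 6.1.11).

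**Assumed, because the protocol gives no values.** Baseline rates above the minimum, the distribution of daily counts, and the between-patient SD of log change.

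**1. The plan's own figure.** The stated 90% power refers to a Wilcoxon-Mann-Whitney test. By Noether's formula, p = Φ(35/(60√2)) = 0.660, and power at 70 per group = Φ(√(6×70) × 0.160 − 1.96) = 90.6%. This reproduces the plan's figure, which does not depend on the offset.

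**2. Offset = days with data.** The expected active-to-placebo ratio is 0.50/0.85 = 0.588, a 41% relative reduction.

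**3. Offset = days with at least one seizure, Poisson daily counts.** With daily mean m, expected seizures per seizure-day are m/(1 − e^(−m)). The baseline term is the same in both arms and cancels. For baseline daily rate λ the ratio is therefore

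[0.50λ/(1 − e^(−0.50λ))] / [0.85λ/(1 − e^(−0.85λ))].

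Worked at λ = 1 (28 per 28 days): 0.50/0.3935 = 1.271; 0.85/0.5726 = 1.484; ratio 0.856.

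**4. The same with overdispersed days.** For negative binomial daily counts with variance m + km², seizures per seizure-day are m/(1 − (1 + km)^(−1/k)). With k = 1 this reduces to 1 + m. At 8 per 28 days that gives (1 + 0.143)/(1 + 0.243) = 0.920.

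| Baseline seizures per 28 days | Days with data | Literal, Poisson | Literal, k = 1 | Literal, k = 3 |
|---|---|---|---|---|
| 8 (entry minimum) | 0.588 | 0.953 | 0.920 | 0.875 |
| 28 | 0.588 | 0.856 | 0.811 | 0.770 |
| 56 | 0.588 | 0.761 | 0.741 | 0.720 |
| 84 | 0.588 | 0.698 | not run | not run |
| 140 | 0.588 | 0.632 | 0.667 | 0.672 |

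**5. Seizure-free patients.** A patient with no seizures on treatment has zero seizure-days, and log(0) is undefined. With days observed, the same patient contributes a count of zero over a positive exposure. For the primary endpoint, criterion 6.1.11 ensures some baseline seizure-days, so only the treatment record is at risk. Subtypes and 'other' seizures have no entry minimum, so for them the baseline record could also be undefined.

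**6. Rough effect on power.** The simulation used 500 trials per setting, 70 per arm, lognormal baselines with medians of 14 to 112 per 28 days, Poisson days, and a t-type test on patient log ratios as a stand-in for the mixed model.

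| SD of log change (assumed) | Power, days with data | Power, literal offset |
|---|---|---|
| 1.0 | 79–88% | 48–77% |
| 0.5 | about 100% | 89–100% |

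Patients with no seizure-days on treatment numbered from 0 to about 1 per two-arm comparison.

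**The case against.** The strongest reply is that the phrase has a second reading and the protocol supports it. Patients or caregivers call the IVRS every day, so each completed call is a seizure report, and a day of reporting can mean a day with a call. Section 13.6.2.1 uses the word that way: an unreported day is a missing day, not a seizure-free one. Amendment 6 names days with data, and it gives patients who withdraw before any seizure as a reason for choosing the model. The literal reading would break the model for exactly those patients. The protocol also plans for patients with no post-baseline seizures in its log-ANCOVA sensitivity analysis. A SAP is due before unblinding and may state the offset correctly; it is not at hand.

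This stands as evidence of intent. A reader might infer from Section 13.6.2 alone that the primary test cannot measure seizure frequency. The documents do not support that: under the evidently intended reading it does, and harm follows only if the sentence is implemented literally.

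It is also fair that the size is uncertain, that the computed bias runs toward no effect so no false claim of efficacy is shown, and that the Wilcoxon, rank ANCOVA and log-ANCOVA analyses do not use this offset and could expose a divergence.

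What does not stand is that the wording can be left alone. The rationale is not superseded text: it explains the very sentence now in Section 13.6.2, and Amendment 7 lists no change to it. Recovering the intent means overriding the plain meaning of the operative sentence, and two competent programmers could produce different primary results. The sensitivity analyses cannot replace test 1.

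**Conclusion.** Wrong as written. Section 13.6.2 conflicts with the Amendment 6 rationale and with the usage in Section 13.6.2.1; the intended offset is evidently days with IVRS data.

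If the literal wording were followed, a planned 41% relative reduction would appear as roughly 5% at the entry minimum (1 − 0.953) and about 37% at 140 seizures per 28 days (1 − 0.632) with Poisson days. With overdispersed days it would appear as about 8% to 33% (ratios 0.92 to 0.67). The entry minimum is the extreme case, not a typical patient. The power loss could be substantial or slight, depending on a between-patient SD that the protocol does not give. Undefined records would probably be few for the primary endpoint and could be more common for subtypes and 'other' seizures.

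**What to change.** In Section 13.6.2, replace the phrase defining the offset with: *the log-transformed number of days with a completed IVRS seizure report (including reports of zero seizures) in the baseline period and in the treatment period*. In Section 13.6.3, state that the same offset applies to every endpoint analysed by the primary method.

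The cost is one sentence in the protocol, a cross-reference, and matching text in the SAP and program specification. No new data are needed, and it should be done before the blinded phase is unblinded.
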